2.2 Secondary

- To determine if administration of prophylactic Defibrotide will prevent the development of TMA in clinically high-risk patients compared to historic controls.
 - Incidence of TMA in the first 6 months post-HSCT will be compared to incidence in a similar cohort of historical controls.
 - Incidence of severe TMA as defined by any TMA with the following complications:
 - Renal dysfunction requiring dialysis
 - Pleural or pericardial effusion requiring any medical or surgical intervention
 - CNS dysfunction including seizure, PRES
 - Death

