7.2 Definitions

7.2.1 Definition of TMA

Criteria for diagnosis of TMA for purposes of this study will be as follows:

- Evidence of microangiopathy, with an additional item from Category A or B, OR
 - The presence of schistocytes (>2/HPF) in the peripheral blood, or
 - Histologic evidence of microangiopathy on a tissue specimen, or

- Undetectable haptoglobin with increased reticulocyte count
- No evidence of microangiopathy but:
 - 1 item from Category A (evidence of organ dysfunction), AND
 - 3 items from Category B (increased TMA biomarkers)

Category A (clinical markers / organ dysfunction)	Category B (biomarkers)

 • Proteinuria • Hypertension • Renal dysfunction 	
 • De novo anemia • Do novo thrombocytopenia • Elevated LDH • Terminal Complement Activation

*Definitions of these criteria are provided below.

Definitions of criteria are adapted from Jodele et al (2015 Blood Rev) and provided below:

Laboratory or clinical marker	Description
1. Lactate dehydrogenase (LDH)	
 • Elevated above the upper limit of normal for age
2. Proteinuria	
 • A random urinalysis protein concentration of ≥ 30 mg/dL or abnormal Pr/Cr Ratio
3. Hypertension	
 • <18 years of age: a blood pressure at the 95th percentile value for age, sex and height. • ≥ 18 years of age: a blood pressure $\geq 140/90$ mm Hg.
4. De novo thrombocytopenia	
 • Thrombocytopenia with a platelet count $< 50 \times 10^9/L$ or a $\geq 50\%$ decrease in the platelet count
5. De novo anemia	
 • A hemoglobin below the lower limit of normal for age anemia requiring transfusion support
6. Evidence of microangiopathy	
 • The presence of schistocytes ($>2/HPF$) in the peripheral blood, or • histologic evidence of microangiopathy on a tissue specimen, or • Undetectable haptoglobin with increased reticulocyte count
7. Terminal complement activation	
 • Elevated plasma concentration of sC5b-9 above upper normal laboratory limit
8. Renal dysfunction	
 • Elevated creatinine above upper limit of normal not due to alternative cause (e.g., drug, fluid status)

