7.2.2 Definition of Severe TMA

Any TMA meeting criteria described in 7.2.1 with any of the following additional features:
• Renal dysfunction requiring dialysis
• Pleural or pericardial effusion requiring any medical or surgical intervention
• CNS dysfunction including seizure
• Inpatient admission > 90 days duration directly related to TMA management

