8.1 Study Endpoints

- Open label non-randomized un-blinded study to determine feasibility, safety, and efficacy.
- Feasibility endpoints;
 - Incidence of discontinuation of defibrotide. Study will be suspended if defibrotide is not tolerated as outlined below:

N (accrued)	0-6	7-12	13-18	19-24
Evaluate if discontinued in this many or more patients:	5	8	10	12

- Safety endpoints
 - Incidence of reportable SAE's (possibly drug-related and severe or unexpected). Study will be suspended if reportable AE's

N (accrued)	0-6	7-12	13-18	19-24
Evaluate if drug-related SAE's occur in this many or more patients:	4	7	10	12

- Incidence of TMA
 - Historical incidence: 7 of 22 (31.8%). With N=24, study will have 80% power to detect a statistically significant difference if incidence in this treated cohort is 8% or less.
 - Study will be re-evaluated if 2 patients develop TMA as this will render the secondary endpoint futile. May continue enrollment to determine feasibility and safety or expand the patient cohort.
- Incidence of Severe TMA
 - Historical incidence: 6 of 22 (27.3%). With N=24, study will have 70% power to detect a statistically significant difference if incidence in this treated cohort is 4% or less.
 - Study will be re-evaluated if 1 patient develops severe TMA as this will render the secondary endpoint futile. May continue enrollment to determine feasibility and safety or expand the patient cohort.

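### The severe-TMA definition in 7.2.2 sets no time order for dialysis, effusion or CNS dysfunction and no cause condition for the last two, and the historical 6/22 was graded by a different rule

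*Combined protocol and SAP*

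**What the plan says.** All references are to the combined protocol and SAP.

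- **7.2.2** defines severe TMA as "Any TMA meeting criteria described in 7.2.1 with any of the following additional features". The features are "Renal dysfunction requiring dialysis", "Pleural or pericardial effusion requiring any medical or surgical intervention", "CNS dysfunction including seizure" and "Inpatient admission > 90 days duration directly related to TMA management". Only the last is tied to TMA.
- **7.2.1** defines renal dysfunction as raised creatinine with alternative causes, such as drugs or fluid status, excluded. 7.2.2 does not say whether that definition carries over to its dialysis item.
- **2.2** gives a parallel definition: "Incidence of severe TMA as defined by any TMA with the following complications". Its list adds PRES and death and omits the long admission. 2.4.2 points to 7.2.2 as the governing criteria.
- **1.3** graded the historical cases as severe on renal failure, pericardial effusion and/or death. Of 22 high-risk patients, 7 had TMA and 6 of those were severe.
- **8.1** states: "Study will be re-evaluated if 1 patient develops severe TMA as this will render the secondary endpoint futile". It then allows enrolment to go on or the cohort to be enlarged.
- **8.2.1** bases the sample size on severe TMA: 28% historically against 4%, alpha 5%, N=24, power 92%.

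**The concern.** Applied as written, 7.2.2 allows a seizure during conditioning, or a treated effusion with another explanation, to turn a later non-severe TMA into a severe one. Because the drafters attached a relation condition to one feature of four, a literal reader will conclude that the others need none. No time window or adjudication step appears elsewhere, and the attribution table in 7.5 concerns the study drug, not TMA.

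The historical rate has a separate problem. It rests on a rule that shares only part of its content with 7.2.2. Renal failure without dialysis, an untreated pericardial effusion, or death could count in 1.3 but is not listed in 7.2.2. Pleural effusion, CNS dysfunction and long admission are listed in 7.2.2 but not in 1.3. With about one severe case expected in the treated group (24 x 4% = 0.96), a single reclassified patient on either side can matter.

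**Working it through.** **1. The plan's own figure.** An exact one-sample binomial test against 28% with N=24 rejects at 2 or fewer cases: P(X<=2 | 24, 0.28) = 0.0196. Power at 4% is P(X<=2 | 24, 0.04) = 93.1%, close to the stated 92%. The 70% stated in 8.1 is instead matched by a one-sided pooled two-sample normal test of 6/22 against 4% in 24 (71.6%). The plan names no test, so both kinds are carried forward.

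**2. Who can be misclassified.** Only a patient whose TMA is not already severe can be upgraded.
- Plan targets (8.1): 8% TMA minus 4% severe = about 4% non-severe.
- Historical (1.3): 7 minus 6 = 1 of 22, or 4.5%.

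**3. Chance of a false severe case.** Let t be the non-severe TMA rate and q the share of those patients with an unrelated or earlier feature. The documents give no q; I assume 5% to 20%. P(at least one in 24) = 1 - (1 - t x q)^24.

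| t | q | t x q | P(at least one) |
|---|---|---|---|
| 0.04 | 5% | 0.0020 | 4.7% |
| 0.04 | 10% | 0.0040 | 9.2% |
| 0.04 | 20% | 0.0080 | 17.5% |
| 1/22 | 5% | 0.0023 | 5.3% |
| 1/22 | 10% | 0.0045 | 10.4% |
| 1/22 | 20% | 0.0091 | 19.7% |

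**4. Effect on the 8.1 trigger.** At a true 4% severe rate, P(at least one case in 24) = 1 - 0.96^24 = 62.5%. With t = 0.04, the observed rate rises to 4.2% at q=5% and 4.8% at q=20%, and the trigger probability to 64% and 69%. Exact one-sample power falls from 93.1% to 92.2% and 89.4%.

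**5. Effect of one case on the test.**

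| Treated | Two-sided Fisher vs 6/22 | Exact one-sided vs fixed 28% |
|---|---|---|
| 0/24 | 0.008 | 0.0004 |
| 1/24 | 0.043 | 0.0039 |
| 2/24 | 0.128 | 0.020 |
| 3/24 | 0.276 | 0.064 |

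**6. Effect of re-scoring one historical case.** With one case removed (5/22), 1/24 gives a two-sided Fisher p of 0.090. With the one non-severe case upgraded (7/22), 1/24 gives 0.020. The documents do not show which way re-scoring would go.

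**The case against.** Counting events without asking their cause is a defensible choice in an open-label, single-arm study: it removes a judgment that unblinded staff could make in the drug's favour, and over-counting in the treated group errs against the drug. This stands, and it is why attribution should not become part of the main definition. It does not defend the missing time order, which can be settled from dates. Nor does it make the comparison conservative overall, because the historical grading also had no attribution condition and used other features.

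The word complications in 2.2 suggests that the features should follow from TMA. It is a weak hint: 2.4.2 sends the reader to 7.2.2, where they are only additional features, and the two lists differ.

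Four stronger inferences are tempting and are not supported:
- **That dialysis has no cause condition at all.** If the 7.2.1 definition carries over, drug- or fluid-related renal failure is excluded. For dialysis, what is missing is a time order and an explicit cross-reference.
- **That false severe cases are likely.** Applying q to all TMA patients at 31.8% incidence would give 32-79%, but most of those historical cases were already severe and cannot be upgraded.
- **That one false case always costs significance.** This holds for the step from 1 to 2 cases under Fisher. It does not hold from 0 to 1, or at 2/24 against a fixed 28%.
- **That one false case stops the trial.** 8.1 prescribes a re-evaluation, which true cases alone would prompt 62.5% of the time at the target rate.

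**Conclusion.** The gap is real and moderate in size. Cause is unaddressed for effusion and CNS dysfunction and arguable for dialysis; time order is unaddressed for all three. With an assumed q of 5-20%, the chance of at least one false severe case is about 5-18% at the plan's targets and 5-20% at the historical non-severe rate. With t = 0.04, misclassification adds roughly 2 to 7 percentage points to the trigger probability. Whether one case alters the significance result depends on a test the plan has not named.

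The mismatch with the historical grading needs no assumption about q: 6/22 and the trial's count are not measured by the same rule, and one historical case either way moves p for 1/24 between 0.020 and 0.090 under Fisher. None of this makes a stated power figure wrong, and the primary endpoints (2.4.1) are unaffected.

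**What to change.** 1. In 7.2.2, count dialysis, effusion or CNS dysfunction only if its onset is on or after the date on which the 7.2.1 criteria are met. Record that onset date on the CRF.
2. State in 7.2.2 that the 7.2.1 definition of renal dysfunction applies to the dialysis item.
3. Align the lists in 2.2 and 7.2.2, settling the status of PRES, death and the admission longer than 90 days.
4. Before the comparison, re-score the seven historical high-risk TMA cases under the same 7.2.2 rule and restate the historical rate in 8.1 and 8.2.1.
5. Report attribution to another documented cause only as a sensitivity analysis, because it is an unblinded judgment.

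The cost is a few sentences, one CRF date field and a re-read of seven charts. The historical rate may become less favourable to the trial. The time-order rule will not remove unrelated events that begin after TMA; the sensitivity analysis addresses those. It could also exclude a feature that starts shortly before the criteria are documented, so features with earlier onset should be listed. The change concerns endpoint classification only and alters no patient's care.

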7.3 Evaluation of Safety and Toxicity

Evaluable for toxicity

All patients will be evaluable for toxicity from the time of their first treatment with the study drug. This includes measuring incidence of hemodynamically significant bleeding or bleeding that results in life-threatening or permanent clinical sequelae.

Analyses will be performed for all patients having received at least one dose of study drug. The study will use the [CTCAE v4.03](#) for reporting of non-hematologic adverse events and modified criteria for hematologic adverse events.

7.4 Definitions of Adverse Events

7.4.1 Adverse Event

An adverse event (also known as an adverse experience) is defined as any untoward medical occurrence associated with the use of a drug in humans, whether or not considered drug related. More specifically, an adverse event (can be any unfavorable and unintended sign (e.g., an abnormal laboratory finding), symptom, or disease temporally associated with the use of a drug, without any judgment about causality. An adverse event can arise from any use of the drug (e.g., off-label use, use in combination with another drug) and from any route of administration, formulation, or dose, including an overdose.

7.4.2 Adverse reaction

An adverse reaction is defined as any adverse event caused by the use of a drug. Adverse reactions are a subset of all suspected adverse reactions for which there is reason to conclude that the drug caused the event.

7.4.2.1 Suspected

A suspected adverse reaction is defined as any adverse event for which there is a reasonable possibility that the drug caused the adverse event. For the purposes of IND safety reporting, "reasonable possibility" indicates that there is evidence to suggest a causal relationship between the drug and the adverse event. A suspected adverse reaction implies a lesser degree of certainty about causality than an adverse reaction.

7.4.2.2 Unexpected

An adverse event or suspected adverse reaction is considered *unexpected* if it is not listed in the investigator brochure or package insert(s), or is not listed at the specificity or severity that

has been observed, or, if an investigator brochure is not required or available, is not consistent with the risk information described in the general investigational plan or elsewhere in the current application.

“Unexpected,” as used in this definition, also refers to adverse events or suspected adverse reactions that are mentioned in the investigator brochure as occurring with a class of drugs or as anticipated from the pharmacological properties of the drug, but are not specifically mentioned as occurring with the particular drug under investigation.

Adverse events that would be anticipated to occur as part of the disease process are considered *unexpected* for the purposes of reporting because they would not be listed in the investigator brochure. For example, a certain number of non-acute deaths in a cancer trial would be anticipated as an outcome of the underlying disease, but such deaths would generally not be listed as a suspected adverse reaction in the investigator brochure.

Some adverse events are listed in the Investigator Brochure as occurring with the same class of drugs, or as anticipated from the pharmacological properties of the drug, even though they have not been observed with the drug under investigation. Such events would be considered *unexpected* until they have been observed with the drug under investigation. For example, although angioedema is anticipated to occur in some patients exposed to drugs in the ACE inhibitor class and angioedema would be described in the investigator brochure as a class effect, the first case of angioedema observed with the drug under investigation should be considered *unexpected* for reporting purposes.

7.4.2.3 Serious

An adverse event or suspected adverse reaction is considered *serious* if, in the view of either the investigator or sponsor (The University of California, San Francisco), it results in any of the following outcomes:

- Death
- Life-threatening adverse event
- Inpatient hospitalization or prolongation of existing hospitalization
- A persistent or significant incapacity or substantial disruption of the ability to conduct normal life function
- Congenital anomaly/birth defect

Important medical events that may not result in death, are life-threatening, or require hospitalization may be considered serious when, based upon appropriate medical judgment, they may jeopardize the patient or subject and may require medical or surgical intervention to prevent one of the outcomes listed in this definition. Examples of such medical events include allergic bronchospasm requiring intensive treatment in an emergency room or at home, blood dyscrasias or convulsions that do not result in inpatient hospitalization, or the development of drug dependency or drug abuse.

7.4.2.4 Life-threatening

An adverse event or suspected adverse reaction is considered *life-threatening* if, in the view of either the investigator or sponsor, its occurrence places the patient or subject at immediate risk of death. It does not include an adverse event or suspected adverse reaction that, had it occurred in a more severe form, might have caused death.

7.5 Recording of an Adverse Event

All grade 3 and above adverse events will be entered into the study database, whether or not the event is believed to be associated with use of the study drug. Safety data (SAEs) will be collected from the time of admission until the day after completion of defibrotide (6-12 times the half-life of the study drug). Data about these events and their severity will be recorded using the NCI CTCAE v4.0.

The Investigator will assign attribution of the possible association of the event with use of the investigational drug, and this information will be entered into the study database using the classification system listed below:

Relationship	Attribution	Description
Unrelated to investigational drug/intervention	Unrelated	The AE is clearly NOT related to the intervention
	Unlikely	The AE is doubtfully related to the intervention
Related to investigational drug/intervention	Possible	The AE may be related to the intervention
	Probable	The AE is likely related to the intervention
	Definite	The AE is clearly related to the intervention

Signs or symptoms reported as adverse events will be graded and recorded by the Investigator according to the CTCAE. When specific adverse events are not listed in the CTCAE they will be graded by the Investigator as *none, mild, moderate* or *severe* according to the following grades and definitions:

- Grade 0 No AE (or within normal limits)
- Grade 1 Mild; asymptomatic or mild symptoms; clinical or diagnostic observations only; intervention not indicated
- Grade 2 Moderate; minimal, local, or noninvasive intervention (e.g., packing, cautery) indicated; limiting age-appropriate instrumental activities of daily living (ADL)
- Grade 3: Severe or medically significant but not immediately life-threatening; hospitalization or prolongation of hospitalization indicated; disabling; limiting self-care ADL
- Grade 4: Life-threatening consequences; urgent intervention indicated
- Grade 5: Death related to AE

7.6 Follow-up of Adverse Events

All adverse events will be followed with appropriate medical management until resolved. Patients removed from study for unacceptable adverse events will be followed until resolution or stabilization of the adverse event. For selected adverse events for which administration of the investigational drug was stopped, a re-challenge of the subject with the investigational drug may be conducted if considered both safe and ethical by the Investigator.

7.7 Adverse Events Monitoring

All adverse events, whether or not unexpected, and whether or not considered to be associated with the use of the study drug, will be entered into the study database, as noted above.

The Investigator will assess all adverse events and determine reportability requirements to the UCSF's Institutional Review Board, the Committee on Human Research (CHR).

All adverse events entered into the study database will be reviewed by the Study Committee on a monthly basis. The Study Committee will review and discuss at each meeting the selected toxicity, the toxicity grade, and the attribution of relationship of the adverse event to the administration of the study drug(s).

All grade(s) 3-5 adverse events entered into the study database will be reviewed on a monthly basis at the Study Committee meetings. The Site Committee will review and discuss the selected toxicity, the toxicity grade, and the attribution of relationship of the adverse event to the administration of the study drug(s).

In addition, all suspected adverse reactions considered "serious" entered into the study database, will be reviewed and monitored by the study committee on an ongoing basis and discussed at study meetings, which take place every eight weeks.

7.8 Expedited Reporting

Reporting to the Data and Safety Monitoring Committee

If a death occurs during the treatment phase of the study or within 30 days after the last administration of the study drug(s) and it is determined to be related either to the study drug(s) or to a study procedure, the Investigator or his/her designee must notify the study Chair (or qualified alternate) within 1 business day of knowledge of the event. The contact may be by phone or e-mail.

Reporting to UCSF Committee on Human Research (Institutional Review Board)

The Principal Investigator must report events meeting the UCSF CHR definition of "Unanticipated Problem" (UP) within 10 business days of his/her awareness of the event.

Expedited Reporting to the Food and Drug Administration

If the study is being conducted under an IND, the Sponsor-Investigator is responsible for determining whether or not the suspected adverse reaction meets the criteria for expedited reporting in accordance with Federal Regulations (21 CFR §312.32).

The Investigator must report in an IND safety report any suspected adverse reaction that is both serious and unexpected. The Sponsor-Investigator needs to ensure that the event meets all three definitions:

- Suspected adverse reaction (as defined in 6.1.30)
- Unexpected (as defined in 0)
- Serious (as defined in 6.1.5)

If the adverse event does not meet all three of the definitions, it should not be submitted as an expedited IND safety report.

The timeline for submitting an IND safety report to FDA is no later than **15 calendar days** after the Investigator determines that the suspected adverse reaction qualifies for reporting (21 CFR 312.32(c)(1)).

Any unexpected fatal or life-threatening suspected adverse reaction will be reported to FDA no later than **7 calendar days** after the Investigator's initial receipt of the information (21 CFR 312.32(c)(2)).

Any relevant additional information that pertains to a previously submitted IND safety report will be submitted to FDA as a Follow-up IND Safety Report without delay, as soon as the information is available (21 CFR 312.32(d)(2)).

Reporting to Pharmaceutical Companies providing Study Drug

- Reporting to Jazz Pharmaceuticals
 - The SI must send all SAEs (initial and follow-up) that require collection and reporting per protocol, and which occur in a subject who received a Jazz Pharmaceuticals product as study drug, to the Jazz Pharmaceuticals Drug Safety Department within 1 business day of their awareness of the SAE ([contact]).
 - The SI will report the SAEs using a US-FDA Form 3500A (MedWatch form). [Note: the MedWatch form, is available at <http://www.fda.gov/downloads/Safety/MedWatch/HowToReport/DownloadForms/UCM082728.pdf>]
 - The SI must also provide Jazz Pharmaceuticals Drug Safety Department ([contact]) with a copy of all submissions made to the FDA at the time the submission is made.
 - In addition, all other adverse events will be reported to the Jazz Pharmaceuticals Drug Safety Department in summary or line-item form upon Jazz Pharmaceuticals' request and at the conclusion of the study.

8 Statistical Considerations and Evaluation of Results

